In Malaysia, there are no specific guideline for prediabetes individual and they are managed according to the latest Clinical Practice Guideline in Malaysia (MOH *et al.*, 2020). For prevention prediabetes to further develop to diabetes, lifestyle intervention such as weight loss (5-10% of initial body weight), regular physical activity (150 min/week), with dietary strategies including reduced calories and behavior modification are recommended in Clinical Practice Guideline in Malaysia (MOH *et al.*, 2020). A high fibre diet (20-30g/day with 5 to 7 servings/day) consisting of vegetables, fruits, legumes and whole grains is encouraged too (MDES, 2020). All the prediabetic individuals will be referred to dietitian and nurse educators for 6 months routine treatment, prior to T2DM diagnosis, determined by second-round of oral glucose tolerance test (OGTT) in 6-month period (MOH *et al.*, 2020). To the puzzlement of many diabetes researchers and clinicians, some of the prediabetes cases showed tremendous improvement in their blood sugar result, yet some of the prediabetes

individuals developed full-blown of T2DM with their blood sugar result higher than the normal range; despite all of them followed the same routine treatment from healthcare clinics. Perhaps, besides the usual routine treatment from Clinical Practice Guideline (MOH *et al.*, 2020) (weight management, physical activity advices and dietary modification); prediabetic individuals who able to improve their blood sugar result in 6-month period has particular meal-timing, compared to those has uncontrolled blood sugar result in 6-month period.

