Those who meet the inclusion criteria will be invited to participate in this study. Eligible participants shall meet all the following inclusion criteria.

- 1) Newly diagnosed prediabetic individuals who have been first seen by clinical dietitian registered under the Ministry of Health Malaysia.
- 2) Malaysian ≥ 18 years old.
- 3) Those who plan to continue prediabetes care at a community clinic in Melaka.
- 4) Those who can read, write and understand the Malay Language.

Participants who meet the following criteria will be excluded from continuing the study.

- 1) Night shift workers at least 3 times per week.
- 2) Known sleep disorder.
- 3) Pregnant Women.
- 4) Those on oral glucose-lowering medications, diabetes supplements, anticonvulsant medications or oral steroids currently or in the last month.
- 5) Those with prior explored to any information regarding time-of-eating/time-of-activity restriction.
- 6) Those with chronic kidney disease. They are excluded as current research lack of evidence to support the accuracy of using 24-hour continuous glucose monitoring system (CGMS) (Freestyle Libre Pro, Abbott, Germany).

Prediabetes and diabetes will be defined according to the latest Clinical Practice Guideline in Malaysia (WHO & IDF, 2006; ADA, 2020; MOH *et al.*, 2020). Diagnosis must be confirmed by measurement of venous plasma glucose (FBG and OGTT) or HbA1c level. Table 1 shows the diagnostic value for diabetes on plasma glucose. Table 2 shows the diagnostic values for prediabetes and diabetes based on OGTT. Table 3 shows the diagnostic values for prediabetes and diabetes based on HbA1c. All the tables are adapted from the Clinical Practice Guideline in Malaysia (WHO & IDF, 2006; ADA, 2020; MOH *et al.*, 2020).

Table 1 The diagnostic value for diabetes on plasma glucose

	Fasting	Random
Venous Plasma Glucose	≥ 7.0 mmol/L	≥ 11.1 mmol/L

In symptomatic individual, one abnormal glucose value is diagnostic.

In asymptomatic individual, 2 abnormal glucose value are required.

Table 2 The diagnostic values for prediabetes and diabetes based on OGTT

OGTT Plasma Glucose Values (mmol/L)		
Category	0 hour	2- hour
Normal	<6.1	<7.8
IFG	6.1-6.9	
IGT	-	7.8-11.0
DM	≥ 7.0	≥ 11.1

IFG= impaired fasting glucose; IGT=impaired glucose tolerance; DM=diabetes mellitus

Table 3 The diagnostic values for prediabetes and diabetes based on HbA1c

	Normal	Pre-diabetes	Diabetes
A1c	<5.6% (38mmol/mol)	5.6-6.2% (38-44 mmol/mol)	≥6.3% (45mmol/mol)

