research assistant using the following questionnaire including (1) Munich Chronotype Questionnaires (MCTQ) (Appendix D), (2) Pittsburgh Sleep Quality Index Questionnaire (PSQI) (Appendix H), (3) Harvard Light Exposure Questionnaire (HLEQ) (Appendix G), (4) International Physical Activity Questionnaire (IPAQ) (Appendix C) and (5) Chrononutrition Profile Questionnaire (CPQ) (Appendix I). Anthropometry measurements including body fat, height, body fat percentage, visceral fat, waist circumference and hip circumference will be measured. Participants are requested to fill up 3-days dietary record (3DDR) (2 weekdays and one weekend day) and the data will be collected in the next visit. Baseline reading of fasting plasma glucose (FPG, OGTT, liver function, and HbA1c) will be retrieved from medical records in the community clinic. Routine treatment will be provided as usual. To minimize the loss of follow-up, phone conversations will be made to ensure the 3-days dietary data is completed.

At the second visit (three months from the baseline), all participants are required to wear a CGMS sensor at the back of their upper arms to measure the 24 hours glucose fluctuation over 14 consecutive days. 3DDR will be given to participants to record their consecutive 3 days dietary record and will be returned after 14 days. After 14 days, participants will return the CGMS sensor at the community clinic. Or alternative way of CGMS sensor collection by an assistant at the participant's home. All questionnaires will be interviewed by a trained research assistant again. Anthropometry measurements including body fat, height, body fat percentage, visceral fat, waist circumference and hip circumference will be measured repeatedly.

At the third visit (six months from the first visit), for FBG, OGTT and HbA1c test, all the readings will be retrieved by the research assistant from the medical record to document the glycemic outcome. The participants will be interviewed by the trained research assistant during all clinic visits using similar questionnaires. All anthropometry measurements (body fat, height, body fat percentage, visceral fat, waist circumference and hip circumference) will be conducted again. 3DDR will be given to record their 3 days dietary intake again and the record progress will be followed up through phone. The original 3DDR will be collected at the routine appointment.

Sample size Calculation:

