Energy and macronutrients analysis of dietary record will be performed using Nutritionist ProTM (Axxya Systems, Stafford, TX, USA), based principally on the Nutrient Composition of Malaysian Food and the food product labels. Energy intake will be compared with estimated basal metabolic rate (BMR) to exclude participants who are under-reporting or overreporting their energy intake in their 3-day food diary. BMR is calculated using standard equations based on sex and age provided by FAO/WHO/UNU (1985) (FAO/WHO/UNU 1985). For participants in a non-dieting population, Torun et al. (1996) proposed that a ratio between energy intake and BMR of less than 1.39 and more than 2.24 be considered as under-reporting and over-reporting respectively. These cut-off points will be applied in the present trial. From the 3-day food diary data, The investigator will investigate the dietary intake as reported on the second day of recording. The second day will be selected over the first one to ensure that participants have also include night-time eating in the records. Compare to the later days, which may have been burdened by increasing exhaustion related to the record-keeping, the second day better represents the habitual dietary intake (Ahola et al. 2019). To investigate the energy and macronutrient intakes over the course of the day, five periods will be performed as follows: night (from 00:00 to 04:49), morning (from 05:00 to 09:59), midday (from 10:00 to 13:59), afternoon (from 14:00 to 16:59) and evening (from 17:00 to 23:59), adapted from Ahola et al. (2019). As these periods differed in their duration, energy intake per hour will also be calculated for each of the five periods. In addition, energy and macronutrient intakes per hour (e.g. intakes reported between 10:00 and 10:59 contributed towards the hour "10:00"). Diet quality will be derived from a 177 food items FFQ at second visit, where the Healthy Eating Index (HEI) will be calculated. This FFQ is adapted from the FFQ used by the Malaysian Adults Nutrition Survey (MANS) 2014 (IPH 2014) (Appendix C). Participants will be required to indicate frequency of foods consumed in the last 1 month. Individual portion size will be asked for each food, and pictures of the various portion size will be

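### The energy intake:BMR exclusion uses limits stated for a non-dieting population in adults whose routine care recommends eating less, and its lower limit cannot tell under-reporting from a true reduction in intake

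*Combined protocol and SAP*

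**What the plan says.** Section 3, Exposure measures, sets the purpose of the energy check: "to exclude participants who are under-reporting or overreporting their energy intake in their 3-day food diary". Under-reporting is a ratio below 1.39 and over-reporting a ratio above 2.24. The limits carry a condition, "For participants in a non-dieting population", and are adopted without further comment: "These cut-off points will be applied in the present trial".

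The Introduction describes routine prediabetes care. It includes "weight loss (5-10% of initial body weight" and says that care "with dietary strategies including reduced calories and behavior modification are recommended". It adds: "All the prediabetic individuals will be referred to dietitian and nurse educators for 6 months routine treatment". The first inclusion criterion in Section 3 is "Newly diagnosed prediabetic individuals who have been first seen by clinical dietitian", and the baseline-visit description says "Routine treatment will be provided as usual".

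The Statistical Analysis section does not mention the exclusion. The plan does not say which diary triggers it, or whether a participant leaves only the diary-based models or the whole study.

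**The concern.** The plan attaches a condition to the limits and then applies them to people whose care works against that condition. Reported intake divided by BMR is low when the report is too low and also when the intake is truly low. The ratio alone cannot separate the two, so an accurate recorder who follows calorie advice can be removed as a mis-reporter.

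Exclusion may then depend partly on adherence to advice. Selecting on intake alone need not bias a correctly adjusted slope. If adherence is also related to glycaemia beyond the listed covariates, selection bias becomes possible in the diary-based associations, for example the timing of the last night meal with its calorie content. Adherence to advice is not among those covariates. Questionnaire exposures (CPQ, MCTQ) would be touched only if the exclusion is study-wide.

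**Working it through.** **1. Does the plan show that the condition holds?** The limits come from a cited source and cannot be re-derived from the documents, so the check is on their stated condition. There is no eligibility criterion on calorie restriction and no dieting question tied to the rule. The repeated weights are not used to interpret a low ratio, and no analysis retains the excluded participants. Appendix E tells participants not to change food habits while recording. That covers the recording days, but a reduced intake may already be the habit.

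**2. How large a true cut crosses the lower limit?** Let r be the habitual intake:BMR ratio and d the proportional cut, with accurate reporting. The recorded ratio is r(1 − d), which falls below 1.39 when d > 1 − 1.39/r. The documents give no value of r, so a range is assumed.

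| Assumed r | 1 − 1.39/r | Cut that crosses 1.39 |
|---|---|---|
| 1.5 | 1 − 0.927 | more than 7.3% |
| 1.6 | 1 − 0.869 | more than 13.1% |
| 1.7 | 1 − 0.818 | more than 18.2% |
| 1.8 | 1 − 0.772 | more than 22.8% |
| 2.0 | 1 − 0.695 | more than 30.5% |

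For example, a true 20% cut from r = 1.7 gives 1.7 × 0.80 = 1.36, which is labelled under-reporting although the diary is correct.

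**3. Can the share excluded, or its direction, be derived?** A simple model was tried with every input assumed: habitual ratio normal with mean r and SD 0.15, and daily intake CV 20% averaged over 3 days (20/√3 = 11.5%). A participant is excluded if the recorded ratio is below 1.39 or above 2.24.

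| Mean r | Nobody cuts | Everyone cuts 10% | Everyone cuts 15% |
|---|---|---|---|
| 1.6 | 19.8% | 42.1% | 57.2% |
| 2.0 | 20.0% | 8.7% | 10.3% |

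At r = 1.6 those who cut are excluded 2.1 to 2.9 times as often as those who do not (42.1/19.8 and 57.2/19.8). At r = 2.0 they are excluded about half as often, because 19.0 of the 20.0 points among non-cutters lie above 2.24 and cutting moves people back inside the limits. Within r = 1.5 to 1.8, moving the SD between 0.10 and 0.30 takes the ratio of cutters to non-cutters excluded from about 1.2 to about 4.6. The answer is set by the assumptions and not by the documents.

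**4. Which diaries are exposed?** The 3- and 6-month diaries follow the start of routine care. For the baseline diary, the places disagree or leave room:
- Location of Research recruits at the first diet-clinic visit and calls this baseline, which suggests a diary before advice.
- The inclusion criterion requires that a dietitian has already seen the participant.
- The visit description hands the diary out at baseline and collects it at the next visit.
- Exposure measures has it taken by interview at baseline.

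The number of diaries also differs: two in Exposure measures, but one at each of three visits in the visit description.

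**The case against.** Advice to eat less is not proof of dieting, and the plan nowhere says that participants restrict intake. That stands. A reader might infer that the cohort is dieting and the limits are therefore wrong for it; the documents support only that the stated condition is not shown to hold.

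A reader might also infer that adherent participants are removed more often than others. Step 3 shows that this can reverse, so it is not claimed. Advice to reduce calories bears on the 1.39 limit only; it does not explain a ratio above 2.24.

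The baseline diary may well precede advice, given recruitment at the first diet-clinic visit. That also stands as a possibility, which the other places leave unsettled.

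The set of affected exposures may be narrow. Even the energy and macronutrient distribution listed under diet quality has an uncertain source, since Exposure measures derives diet quality from a food frequency questionnaire and then scores it from the diet record.

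Finally, replacing the prespecified exclusion with full inclusion would trade a possible selection effect for known mis-reporting in the exposure, at a time when analysis was already scheduled. This is a fair objection to changing the main analysis, but it does not count against showing both results.

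**Conclusion.** The point holds in limited form. A stated rule can classify truthful low-intake diaries as mis-reported, and no analysis in the plan would reveal whether that matters. The firm figures are the cuts that cross 1.39, about 7% to 31%. They rest only on an assumed habitual ratio of 1.5 to 2.0 and accurate reporting.

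The documents do not give the share excluded. Nor do they settle whether those who cut are over- or under-represented among the excluded, or the direction and size of any bias. A reader might also infer a loss of power; without the share excluded or the scope of the rule, that cannot be supported. Exposure to the problem is clearest at 3 and 6 months and open at baseline.

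**What to change.** - Keep the prespecified exclusion as one analysis. State that it applies only to diary-based models, and name the diary that triggers it.
- Add a sensitivity analysis that retains all participants with a diary. Report the two sets of results side by side, with the number below 1.39 and the number above 2.24 at each visit. Temper the diary-based conclusions if the two sets differ.
- Reconcile the inclusion criterion, Location of Research, the visit descriptions and Exposure measures on when the baseline diary is recorded and how many diaries there are.
- Date the addition. Section 4 schedules data entry and analysis from 07/03/2024 to 06/09/2024 and the document is dated 6 May 2024, so report the change as made during the scheduled analysis period.

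The cost is SAP wording and one further set of model runs on data already scheduled for collection. The downside is that the retained set includes some genuine mis-reporters, which is why it sits beside the exclusion analysis and does not replace it.

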The FreeStyle Libre Pro CGM system consists of a disposable sensor, an applicator, and a reader; that is used to start the sensor on the participant and gather the glucose data at the end of the CGMS period. The Sensor can be worn for up to 14 days, on the back of their upper arm (Figure 7). Once applied, a sensor will measure and store glucose readings every 15 minutes. The 24-hour CGMS does not require any participant action as calibration for the sensor is not needed. Readings from the 24-hour CGMS will not be made available to participants in real time, hence, it will prevent the bias that may arise from unmasked real-time glucose readings. The data from all the 24-hour CGMS (Freestyle Libre Pro, Abbott, Germany) sensors is easily accessible through the FreeStyle Libre Pro Software or The LibreView Cloud. In the present study, the 24-hour CGMS reading will be taken 14-day prior to second visit/second-round OGTT reading. All the data from 24-hour CGMS will be analyzed to

investigate to obtain the optimal-meal-timing. The 24-hour CGMS data will be match with 3-day food diary too.

Exposure measures Meal-timing and chrononutrition

At the baseline visit, the researcher will guide the participants to fill out the 3-day food diary covering two weekdays and one weekend day (consecutive Sunday-Tuesday or Thursday-Saturday). Three-day food diary will be taken twice in the entire study. At the baseline visit, 3-day food diary will be interviewed by researcher to the participants. This food diary data will be served as baseline meal-timing data. Subsequently, participant will be given another 3-days daily dietary at second visit, 14-day prior to third visit. Participants are required to record the time, type, description and number of foods and beverages consumed throughout the day. Brand information, ingredients and cooking method will be recorded where applicable, particularly for home-cooked food. Pictures of household measuring utensils and various food portion sizes are printed in the food diary to assist participants in quantifying their food intake. For 14 day return the CGMS, researcher will be interviewed participants on the completeness of 3 days daily dietary intake.

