pattern from the validated questionnaires PSIQ and light exposure from the validated questionnaire HLEQ.

Statistical Analysis

All data will be performed statistical analysis using the SPSS software version 20 (SPSS Inc., Chicago, IL, USA). The socio-demographic will be presented as mean, standard deviations, median, interquartile range, frequency, and percentage. Data cleaning will be performed to exclude the outlier data before the normality is checked using Kolmogorov-Smirnov Test. The investigator considered $p < 0.05$ to be statistically significant. Chronotype, sleep quality, and light exposure will be analyzed as categorical variables whereas dietary intake, chrononutrition, anthropometry, glycemic measure, and physical activity will be analyzed as continuous variables.

The investigator will perform a multivariable generalized linear model to examine the association between night meal pattern (last night mealtime either dinner or supper with calories intake, frequency of night snacking, and the total number of the night snacking) and glycemic outcome (HbA1c, FPG, 2hPPG, CGM profile) by adjusting for the potential covariates. Specifically, nighttime will be characterized by the time range from 1900 and 0659 hours based on Malaysia solar time. The investigator will explore the late-night meal timing in 2000, 2100, and 2200 to examine its association with glycemic outcomes. The potential confounders include sociodemographic characteristics, physical activity, sleep pattern, sedentary behavior, diet quality, and light exposure will be controlled. ANCOVA test will be performed to understand the association between chrononutrition (breakfast skipping, meal frequency, eating window, sleep timing, chronotype, and fasting pattern) with glycemic variables, controlling for potential covariates (sociodemographic characteristics, light exposure, diet quality, physical activity and sleep pattern).

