2.1 Have you smoked in the past?

0: Not at all for entire life

1: Yes, but stopped smoking before conceiving for this pregnancy

2: Yes, but stopped smoking since conceived for this pregnancy

3: Yes, but stopped smoking 1 month ago

4: Yes, during the past 1 month and/ or currently smoking

2.2 During the **past 1 month**, did anyone **smoke in indoor areas** where you work and/ or stay? (Excluding area which are not fully enclosed. Should answer 'yes' if smelling the smoke).

0: No

1: Yes

2.3 How often did you have a drink containing **alcohol** during the **past 3 months before conceiving** for this pregnancy? (Including traditional wine, e.g. Youmeishu, DOM Benedictine)

0: never or less than once per month

1: 1-3 times per month

2: 1-2 times per week

3: 3-4 times per week

4: 5-6 times per week

5: 1 time or more per day

2.4 Have you consumed any drink containing **alcohol since your current pregnancy**? (Including traditional wine, e.g. Youmeishu, DOM Benedictine)

0: No

1: Yes, but stopped drinking 1 month ago

2: Yes, current and during the past 1 month

2.5 Did you take any pills, tonics or tablets to **supplement** your diet (e.g. vitamin, minerals, iron tablets, folic acid, fish oils etc.)? (can be more than 1 options, except if selecting 'Never')

0: Never or without supplement for at least 3 months ago before conceiving for this pregnancy

1: Yes, since 3 months before conceiving for this pregnancy
 2: Yes, since conceived for this pregnancy
 3: Yes, current and during the past 1 month

2.6 **During the past 1 month**, how often did you **skip** your breakfast, lunch and dinner?

	Breakfast	Lunch	Dinner
--	-----------	-------	--------

0: never
 1: 1-3 times per month
 2: 1-2 times per week
 3: 3-4 times per week
 4: 5-6 times per week
 5: Every day

2.7 **During the past 1 month**, how often did you **delay** your breakfast, lunch and dinner for more than 2 hours from your regular meal timings?

	Breakfast	Lunch	Dinner
--	-----------	-------	--------

0: never
 1: 1-3 times per month
 2: 1-2 times per week
 3: 3-4 times per week
 4: 5-6 times per week
 5: Every day

2.8 **During the past 1 month**, how often did you have **snack(s) taken after 7pm**? (Snack is defined as a portion of food often smaller than a regular meal, including beverage such as milk. Snacking frequency is defined with a time interval between episodes of at least 15 min)

0: never

1: 1-3 times per month
 2: 1-2 times per week
 3: 3-4 times per week

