APPENDIX E

Project Name:

Date of interview:

[figure not shown]
Three Days Dietary Record

Meal Timing and Glucose Tolerance

		/				/					60
d	d		m	m	m		y	y	y	y	

61 3 days dietary record guidelines:

[figure not shown]
1. Please fill in this food intake log book as completely as possible for 2 weekdays and 1 weekend.
2. Subjects were not allowed to change food habits while food intake records were being conducted.
3. For food records, please indicate the time, type and quantity/ size of all food and beverages taken immediately after meal time.
4. If you have any further enquiry, please contact:
 [name] [name] [contact]

71 Household Measurements
A) Spoons

84 Teaspoon Table Spoon Table Spoon
 10ml 10ml 10ml
 85 Scoop 30ml Scoop 15ml Scoop 80ml Table Spoon
 86 20ml

B) Plate and Bowls

97
 98
 99
 100
 101
 102
 103
 104
 105
 106
 107
 108
 109
 110
 111
 112
 113
 114
 115
 116
 117
 118
 119
 120
 121
 122
 123
 124
 125
 126
 127
 128
 129
 130
 131
 132
 133
 134
 135
 136
 137
 138
 139
 140
 141
 142
 143
 144
 145
 146
 147
 148
 149
 150
 151
 152
 153
 154
 155
 156
 157
 158
 159
 160
 161
 162
 163
 164
 165
 166
 167
 168
 169
 170
 171
 172
 173
 174
 175
 176
 177
 178
 179
 180
 181
 182
 183
 184
 185
 186
 187
 188
 189
 190
 191
 192
 193
 194
 195
 196
 197
 198
 199
 200
 201
 202
 203
 204
 205
 206
 207
 208
 209
 210
 211
 212
 213
 214
 215
 216
 217
 218
 219
 220
 221
 222
 223
 224
 225
 226
 227
 228
 229
 230
 231
 232
 233
 234
 235
 236
 237
 238
 239
 240
 241
 242
 243
 244
 245
 246
 247
 248
 249
 250
 251
 252
 253
 254
 255
 256
 257
 258
 259
 260
 261
 262
 263
 264
 265
 266
 267
 268
 269
 270
 271
 272
 273
 274
 275
 276
 277
 278
 279
 280
 281
 282
 283
 284
 285
 286
 287
 288
 289
 290
 291
 292
 293
 294
 295
 296
 297
 298
 299
 300
 301
 302
 303
 304
 305
 306
 307
 308
 309
 310
 311
 312
 313
 314
 315
 316
 317
 318
 319
 320
 321
 322
 323
 324
 325
 326
 327
 328
 329
 330
 331
 332
 333
 334
 335
 336
 337
 338
 339
 340
 341
 342
 343
 344
 345
 346
 347
 348
 349
 350
 351
 352
 353
 354
 355
 356
 357
 358
 359
 360
 361
 362
 363
 364
 365
 366
 367
 368
 369
 370
 371
 372
 373
 374
 375
 376
 377
 378
 379
 380
 381
 382
 383
 384
 385
 386
 387
 388
 389
 390
 391
 392
 393
 394
 395
 396
 397

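### Diary-based energy and macronutrient intake by clock period and hour rests on day 2 of each 3-day diary, one weekday, with no planned analysis using all three days

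*Combined protocol and SAP*

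**What the plan says.** In section 3 of the protocol, under the exposure measures for meal timing and chrononutrition, the baseline diary covers "two weekdays and one weekend day (consecutive Sunday-Tuesday or Thursday-Saturday". For the second visit, the methodology text says "3DDR will be given to participants to record their consecutive 3 days dietary record". The form in Appendix E asks: "Please fill in this food intake log book as completely as possible for 2 weekdays and 1 weekend". The form does not itself require the days to be consecutive.

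The exposure section then narrows the analysis: "The investigator will investigate the dietary intake as reported on the second day of recording". Directly after this it defines five clock periods, energy per hour within each period, and energy and macronutrients by clock hour. It gives two reasons for day 2. Against day 1: "The second day will be selected over the first one to ensure that participants have also include night-time eating in the records". Against later days, which may suffer from tiredness with record-keeping, it holds, citing a published study, that "the second day better represents the habitual dietary intake".

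The whole diary is mentioned in two other places. The screen for under- and over-reporting (energy intake against basal metabolic rate) refers to the 3-day diary. The continuous glucose data are to be matched with the 3-day diary, without saying which days or how.

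The Statistical Analysis section lists among its night-meal exposures "last night mealtime either dinner or supper with calories intake". It does not name the source of those calories.

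**The concern.** The diary appears to be the only instrument that shows how much is eaten at what time. The Chrononutrition Profile Questionnaire (Appendix I), the Appendix B items, such as the frequency of "snack(s) taken after 7pm", and the light-exposure form with its circled meal hours (Appendix G) give times or frequencies, not amounts. The food frequency questionnaire is described in terms of frequency and portion, not clock time.

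Three days are collected per diary and one is tabulated. A single day is a noisy measure of what a person habitually eats in, say, the evening. A single weekday also says nothing about the weekend, which is 2/7 of the week. In a regression on one exposure, random day-to-day error pulls the slope towards zero. In the planned multivariable models the direction of bias is not guaranteed. If the night-meal calories are taken from the diary, a leading exposure in the glycaemia models rests on one weekday per diary.

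**Working it through.** **Which weekday is day 2?** All seven runs of three consecutive days:

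| Run | Weekend days | Day 2 |
|---|---|---|
| Mon-Wed | 0 | Tue |
| Tue-Thu | 0 | Wed |
| Wed-Fri | 0 | Thu |
| Thu-Sat | 1 (day 3) | Fri |
| Fri-Sun | 2 | Sat |
| Sat-Mon | 2 | Sun |
| Sun-Tue | 1 (day 1) | Mon |

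Only Thursday-Saturday and Sunday-Tuesday contain exactly one weekend day. These are the two runs that the protocol names for baseline. In both, day 2 is a weekday and the weekend day is day 1 or day 3. For the second-visit diary the conclusion needs consecutive days (methodology text) together with the 2:1 day mix (diary form).

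**How much noisier is one day than three?** The plan gives no figure to reproduce here, and no day-to-day variance. The inputs below are assumptions:

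- single-day intraclass correlation ρ of 0.3, 0.5 or 0.7;
- days equally valid, with zero-mean errors of equal variance;
- weights of 5/14 for each weekday and 4/14 (that is, 2/7) for the weekend day, so that weekdays and weekend count 5:2.

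Reliability = ρ / (ρ + (1 − ρ)v), where v is the error variance of the weighted mean relative to one day. For one day v = 1 and reliability = ρ.

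- Independent errors: v = (25 + 25 + 16)/196 = 66/196 = 0.3367.
- Error correlation 0.3 between adjacent days and 0.09 at lag two, weekend day first or last: v = (66 + 2 × 0.3 × (20 + 25) + 2 × 0.09 × 20)/196 = 96.6/196 = 0.4929.
- Same correlations, unweighted mean: v = (3 + 4 × 0.3 + 2 × 0.09)/9 = 4.38/9 = 0.4867.

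| ρ (one day) | 5:2 mean, independent | Ratio to one day | 5:2 mean, correlated | Ratio to one day |
|---|---|---|---|---|
| 0.3 | 0.560 | 1.87 | 0.465 | 1.55 |
| 0.5 | 0.748 | 1.50 | 0.670 | 1.34 |
| 0.7 | 0.874 | 1.25 | 0.826 | 1.18 |

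Example: 0.3/(0.3 + 0.7 × 0.3367) = 0.560, and 0.560/0.30 = 1.87. For a small effect and a single exposure, this ratio is roughly the ratio of sample sizes needed. The unweighted mean with correlated errors gives 0.468, 0.673 and 0.827. The gain therefore comes from using three days; the 5:2 weights serve to represent the week.

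**What could the weekend do?** If weekend and weekday intake in a period differ by D, the seven-day mean is the weekday mean plus 2D/7. For an assumed D of 50 to 300 kcal this is 14 to 86 kcal. A D shared by all participants shifts the level and leaves a linear slope unchanged. Only a D that varies between participants adds exposure error, and the documents do not say how much it varies.

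**The case against.** The strongest reply is that day 2 was chosen with reasons and a citation, to avoid reporting bias, and that the weekend day is always one of the two days that the protocol distrusts. The reliability figures treat all days as equally valid, so they set aside the very problem that the protocol was guarding against. A three-day mean could be more reliable and yet less valid. This stands. It is why the planned analysis should not be replaced. It does not remove the gap: missed night-time eating on day 1 and fatigue on day 3 are no answer to single-day noise or to weekday-weekend differences.

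A second reply is that participants complete more than one diary, so noise could be averaged over visits. The plan does not say that diaries are combined. If two were, with independent errors, v would be 1/2 for one day from each and 0.3367/2 = 0.1684 for three days from each. The ratio would then fall to 0.718/0.462 = 1.56 at ρ = 0.3 and to 0.933/0.824 = 1.13 at ρ = 0.7. The gain is smaller but still there.

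A third reply is that the Statistical Analysis section names neither the five periods nor hourly intake as a model exposure, and that most of its exposures could come from questionnaires. That is fair. The effect on the glycaemia models depends on whether the night-meal calories come from the diary.

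A reader might infer that the weekend diary day is never used, or that no weekend meal timing is collected. The documents support neither. The glucose matching and the misreporting screen refer to the 3-day diary, and the Chrononutrition Profile Questionnaire asks separately for eating times on weekend or free days.

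**Conclusion.** The concern holds within limits. As written, diary-based energy and macronutrient intake by period and by hour comes from one weekday per diary, and no analysis using all three days is specified for it. This is a weakness in a reasoned choice, not a contradiction in the plan.

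Its size can only be illustrated: reliability of 0.30 to 0.70 for one day against 0.56 to 0.87 (independent errors) or 0.47 to 0.83 (correlated errors) for three. These ranges rest on the assumed intraclass and error correlations and on there being no systematic day-1 omission or day-3 fatigue. They do not measure a weekend effect.

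Two further inferences would go too far. One is that the study is underpowered for this reason: no power figure follows, because the documents give neither the day-to-day variance nor the source of the modelled exposures. The other is that the associations must be biased towards zero, which the planned multivariable models do not guarantee.

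**What to change.** Keep the day-2 analysis as planned. Add a specified analysis of the same diary-based exposures: energy and macronutrients by period and by hour, and night-meal calories if these are taken from the diary. Use the mean of all three days, with 5/14 for each weekday and 2/7 for the weekend day.

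Leave out day 1's after-midnight period where recording began after it. For that period, Sunday-Tuesday diaries then use Monday and Tuesday equally, and Thursday-Saturday diaries use Friday (5/7) and Saturday (2/7). With independent errors and ρ of 0.3 to 0.7, reliability there is 0.46 to 0.82 (v = 0.500) and 0.42 to 0.80 (v = 29/49 = 0.592).

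Report both analyses and say whether conclusions depend on the choice. State in the Statistical Analysis section whether the night-meal calories come from the diary. The document is dated 6 May 2024 and its schedule ends third-visit collection on 06/03/2024, so the added analysis should be labelled post hoc if outcome data have already been examined.

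The cost is a paragraph of analysis plan and the same tabulation for days 1 and 3; no new data are needed. The limitation is that the weekend day is always day 1 or day 3 in the consecutive runs. A difference from day 2 cannot separate a weekend effect from day-1 omission or day-3 fatigue.
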